# 6 RANDOMISATION AND BLINDING

## 6.1 Randomisation Details

After the patient has provided written consent to participate in the study and eligibility has been confirmed, the member of the local research team will randomise the participant via the Clinical Trials Unit (CTU). The CTU is the Centre for Healthcare Randomised Trials (CHaRT) based within the University of Aberdeen. The CTU provides a 24 h randomisation web based service. Using a computer generated sequence, participants will be allocated to receive either of the two treatments or usual care (1:1:1 ratio). Randomisation will be minimised by diagnosis (RA, SLE, AxSpA or other IRD) and the presence/absence of depressive symptoms (Hospital Anxiety & Depression Scale (HADS) depression subscale >10) and will include a random element set at 20%. That is, 20% of all the allocated randomisations will be randomly re-allocated 50:50 to the remaining two treatment options.

Randomised participants will be contacted by the study co-ordinator (or designated deputy if unavailable) by post, email and/or telephone with information about their intervention and details of their allocated therapist, if applicable. All personal contact details will be only accessible in the password protected study database (see 8.2).

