*Mediation analysis:* We will use modern causal inference methods to investigate the set of mediator measures. If the effectiveness analysis shows significant between group differences in the mediators then we will use parametric regression models to test for effect of mediator on outcome, and the residual direct effect of treatment on outcome. Since all the measures are continuous, the indirect effects are calculated by multiplying relevant pathways and bootstrapping is used to produce valid standard errors for the indirect effects. All analyses will adjust for baseline measures of the mediators, outcome and putative measured confounders, and be tested for moderation by diagnosis. Mediation analyses are potentially biased by measurement error in mediators and hidden confounding between mediators and outcomes; we will build on our previous methodological and applied work in this context to include repeated measurement of mediators and outcomes to account for classical measurement error and baseline confounding. We will investigate the sensitivity of the estimates to these problems and that of unmeasured confounding using instrumental variable (IV) methods with baseline covariate by randomisation interactions as potential instruments.

*Moderation analysis:* We will examine differential treatment effects using the set of moderator measures by extending the intention to treat analysis models to include an interaction term between treatment and each of the moderators separately. We will use bias correction/cross-validation methods to identify robust evidence for individual moderation and for a moderation index, both on the overall effect and also along the steps of the mediation pathway.

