#### Analysis

Following pre-processing of the MRI data the following analysis will be undertaken which will integrate data which will have been collected as part of the parent trial:

Longitudinal comparisons (paired t-tests as implemented by SPSS for ROI based variables and Freesurfer for voxel based variables) of structural and functional change indices in relation to subjects' change in fatigue will be performed. Putative confounders will be individually introduced as co-variates of interest. The individual analyses will focus upon those regions of interest previously identified by our studies, but since we recognise that these are not comprehensive we will also conduct agnostic (data-driven) whole brain analyses. All analyses will be adjusted for multiple testing.

Having identified and validated key neural areas, group differences in mediators of treatment effects on outcomes will be assessed via mediation analysis methods in order to tackle the secondary objective. These involve causal inference methods, such as structural equation modelling, to account for measurement error in the imaging data, and repeated measures to allow for the inclusion of all available data. Those resultant neural mediators which are common to both interventions and accessible to non-invasive neuromodulation will serve as our future therapeutic targets.

Finally we will be using whole brain statistical pattern recognition techniques on the neuroimaging data and mediation effects identified in answer to the previous objective. In the Pattern Recognition for Neuroimaging Toolbox (PRoNTo) brain scans are treated as spatial patterns and statistical learning models are used to identify statistical properties of the data that can be used to discriminate between, or classify, experimental groups of subjects.

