#### Sample size

We aim to recruit 120 participants (who will have been randomised to receive either usual care alone, CBA in addition to usual care or PEP in addition to usual care in the parent trial).

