11.2 Statistical Analysis

LIFT has repeated measures on individual participants nested within site suggesting a multilevel model with an appropriate link function depending on the outcome. The analysis will adjust for the outcome variable at baseline as a covariate (when available) as well as the design factors also at baseline [diagnosis (RA, SLE, AxSpA or other IRD), the presence/absence of depressive symptoms HADS depression subscale >10)]. Centre clustering will be accounted for using a random effects robust variance.

11.2.1 Primary Outcome - Effectiveness Analysis.

We will test the primary hypothesis for between-group change in the primary outcome for each of the two pre-specified comparisons (CBA + usual care vs usual care alone and PEP + usual care vs usual care alone) using treatment and its interaction with time fitted as fixed effects, and we apply standard regression diagnostics. The main analysis will focus on the 56 weeks after baseline – providing effect sizes for each of the active arms compared to usual care. Standard regression diagnostics will be applied.

A Complier Average Causal Effect (CACE) analysis will be considered as a sensitivity analysis. Patent engagement & adherence (therapist view) at 8 weeks forms the CACE variable (if missing the 4 weeks reported value will be substituted) as a continuous instrumental variable in the CACE analysis

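### The MRI sub-study (Protocol Appendix 2) introduces confounders one at a time and states no joint model, so each brain–fatigue estimate keeps the confounding from factors outside that model

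*Protocol*

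**What the plan says.** The Analysis section of Protocol Appendix 2 has an association step followed by a mediation step.

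- **Association step.** The method is "Longitudinal comparisons (paired t-tests as implemented by SPSS for ROI based variables and Freesurfer for voxel based variables"), applied to brain change in relation to fatigue change. On confounding it says only: "Putative confounders will be individually introduced as co-variates of interest". On multiplicity: "All analyses will be adjusted for multiple testing". No method of correction is named.
- **Mediation step.** Regions identified and validated in the first step go on to mediation analysis. "These involve causal inference methods, such as structural equation modelling, to account for measurement error in the imaging data". Covariates are not named. Mediators shared by both interventions and reachable by non-invasive neuromodulation become the future targets.
- **Sample.** "We aim to recruit 120 participants", drawn from all three arms. All consenting LIFT participants are invited, so diagnoses are mixed.

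Elsewhere in the documents:

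- Protocol 6.1: "Randomisation will be minimised by diagnosis (RA, SLE, AxSpA or other IRD) and the presence/absence of depressive symptoms".
- Protocol 10.2, on the parent trial's mediation analysis: "All analyses will adjust for baseline measures of the mediators, outcome and putative measured confounders".
- SAP 11.2 adjusts the treatment-effect models for the baseline outcome "as well as the design factors also at baseline", meaning diagnosis and HADS depression above 10.
- SAP 11.3 enters both of those factors together in the mediator model and in the outcome model.
- The SAP introduction limits its scope to the main trial and does not mention the MRI sub-study.

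**The concern.** Brain change and fatigue change are both observed, so randomisation does not protect the association between them. A model with one confounder removes that confounder's contribution and leaves the others in place. A set of such models, each adjusted for something different, can look like a thorough check although no estimate in the set is free of the remaining confounding.

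The documents themselves point to several plausible shared causes:

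- **Depressive symptoms.** The Appendix 2 background reports strong links between fatigue and mental health.
- **Diagnosis.** The sample spans RA, SLE, AxSpA and other IRDs.
- **Randomised arm.** The trial's hypothesis is that CBA and PEP reduce fatigue, and the second scan is timed for when the interventions are expected to have most effect. If treatment changes both brain and fatigue, arm is a common cause.

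At stake is which regions enter the mediation step. The other safeguards do not address this. Multiplicity control limits chance findings but does not remove bias. The validation is not described, and repeating a confounded association in the same sample would reproduce it.

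**Working it through.** **The plan's own figure.** The sample size of 120 comes with no significance level, power or effect size, so it cannot be reproduced. It is used below only as n.

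**Assumed model.** The documents give no confounder strengths, so every strength here is an assumption. Let brain change X and fatigue change Y each have variance 1. Each equals r times the sum of k independent standard confounders plus independent noise, with no direct link between X and Y. Then:

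- variance of each change explained by all confounders = k r²
- correlation of X and Y given one confounder = (k − 1) r² / (1 − r²)
- correlation of X and Y given all k confounders = 0

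**Benchmark.** With n = 120 and one covariate there are 117 degrees of freedom and the two-sided 5% critical t is 1.980. The critical partial correlation is 1.980 / √(1.980² + 117) = 0.180.

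**Results, n = 120, unadjusted 5% level.** The last column is the simulated share of runs in which the null region is significant in all k single-confounder models.

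| k | r | Variance explained, k r² | Remaining correlation, one adjusted | Significant in all k models |
|---|---|---|---|---|
| 5 | 0.10 | 5% | 4 × 0.01 / 0.99 = 0.040 | about 5% |
| 2 | 0.20 | 8% | 1 × 0.04 / 0.96 = 0.042 | about 5% |
| 3 | 0.20 | 12% | 2 × 0.04 / 0.96 = 0.083 | 9% |
| 2 | 0.30 | 18% | 1 × 0.09 / 0.91 = 0.099 | 12–14% |
| 5 | 0.20 | 20% | 4 × 0.04 / 0.96 = 0.167 | about 31% |
| 5 | 0.25 | 31% | 4 × 0.0625 / 0.9375 = 0.267 | about 73% |
| 5 | 0.30 | 45% | 4 × 0.09 / 0.91 = 0.396 | 98–99% |

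The jointly adjusted model gives about 5% in every row.

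**Variations.**

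- *Fewer scans.* If the parent trial's 20% dropout applied, n = 120 × 0.80 = 96. With five confounders the rates are about 24% at r = 0.20 and 94–96% at r = 0.30.
- *Correlated confounders.* With two confounders, each with standardised effect 0.4 on both changes and mutual correlation 0 to 0.6, the rate at n = 120 is 33–45%, against about 5% jointly.
- *Stricter threshold.* At an assumed p < 0.0025, the 31% (five at r = 0.20) falls to about 5%. That is still 0.05 / 0.0025 = 20 times the nominal rate.

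**The case against.** The strongest reply has five parts.

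1. *The confounders are unnamed, not excluded.* A reader might infer that diagnosis and depressive symptoms are never adjusted for. The text does not say so. Both are parent-trial variables that Appendix 2 intends to draw on, and either may be among the putative confounders. Being a minimisation factor also does not make a variable a confounder of this non-randomised association. All this stands. What remains is that, entered individually, the two would not be in a model together.

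2. *The parent trial's models are not the counterpart of this step.* Protocol 10.2 (mediation) and SAP 11.3 correspond to the later mediation step, and SAP 11.2 concerns treatment effects. This stands. Protocol 3.3 lists neuroimaging as mediator/moderator data, so the 10.2 commitment may cover the MRI mediation. The documents do not settle this.

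3. *No selection rule is stated.* A reader might infer that a region is kept if it survives every single adjustment, and hence that false correlates will pass as robust. Appendix 2 gives no such rule, and targets are chosen only after mediation. This stands, so the simulated rates illustrate a mechanism and do not forecast how the sub-study will perform.

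4. *The size depends on the assumptions.* The excess vanishes for weak or few confounders, and the planned multiplicity adjustment would lower the rates. This stands, but correction leaves the bias in each estimate untouched.

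5. *The wording could mean cumulative entry into one model.* That is possible. It is not the natural reading, and since a paired t-test takes no covariates, the model would still be unspecified.

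**Conclusion.** The point holds in limited form. Appendix 2 states one-at-a-time introduction of unnamed confounders and gives no joint model for the association step. Its named test cannot hold covariates, and the SAP does not fill the gap. Each estimate produced this way keeps confounding from every factor outside its model.

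The size cannot be fixed from the documents. Under the assumptions above, the consequence ranges from none to near-certain false significance. It depends on how many confounders there are, how strong they are, whether they act in the same direction, and the significance threshold.

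The documents do not support the stronger conclusions that the minimisation factors are left out or that false regions will be carried forward as targets. The severity is minor: this is an optional, observational, mechanistic sub-study, and the primary comparison of CBA or PEP with usual care is not affected.

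**What to change.** Replace the confounder sentence in Appendix 2 with one pre-specified regression of fatigue change on brain change. It should include, jointly, baseline fatigue, the baseline imaging value, randomised arm, diagnosis, HADS depression above 10 and a short named set of further confounders, for example age, baseline pain and self-reported disease activity. Keep single-confounder models as descriptive only. State whether the SAP 11.3 covariates apply to the MRI mediation step.

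Cost in degrees of freedom: baseline fatigue 1, baseline imaging 1, arm 2, diagnosis 3 and HADS depression 1 make 8. Three further single-term confounders bring it to 11, out of about 120 participants. The trial or sub-study already collects all these variables, so the change is a short text amendment with no new data.

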#### Sample size

We aim to recruit 120 participants (who will have been randomised to receive either usual care alone, CBA in addition to usual care or PEP in addition to usual care in the parent trial).

#### Data handling

MRI scan data will be stored in an anonymised format in the University of Aberdeen, Edinburgh and Glasgow imaging archive system on the university drive, with a back-up disc stored in a fireproof safe. The code for the images will be held on a separate computer relating the patient information to the participant ID. The participant ID will be used on the MRI images. Images may be stored on disc in anonymised format for research team discussions out-with the imaging department.

#### Safety assessments

The MRI scanner is very safe and does not expose participants to any harmful radiation. Given its reliance on a strong magnetic field, it is essential that certain metallic instruments/objects are not taken into the scan room.

This is avoided by:

1) All participants are clothed in 'theatre greens' so to avoid the danger of concealed metal objects within clothes.

2) Patients will be screened for absolute exclusion to MRI scanning.

In addition, all participants must undertake a strict and comprehensive checklist prior to scanning. This includes questions about heart valves, pacemakers and other potential metallic implants.

If a participant becomes distressed during the MRI scan, he/she will be able to access to a "panic button" which will immediately terminate the procedure.

#### Sub-study matrix

The study connects to the 1-year LIFT recruitment phase which will begin in August 2017 (month 0).

Study steps	-3-0 m	0-6 m	6-12 m	12-18 m	18-24 m	24-30 m
Governance						
approvals						
RA Subject						
recruitment						
MRI scan #1						
(pre-intervention)						
MRI scan #2						
(post-intervention)						
Data processing,						
analysis & report						

# Appendix 3: Qualitative Evaluation (LIFT sub-study)

#### Background

Qualitative studies nested within trials offer the opportunity to investigate the views and experiences of participants. They can generate insights into unexpected or unanticipated outcomes of the trial, as well as provide detailed, personal accounts that can aid understanding and implementation of the research.

#### Sub-study Objectives

To understand patients' experiences and views of taking part in the CBA and PEP interventions as part of the LIFT trial.

To explore patients' experiences and views that may have led to participants not engaging with the allocated intervention.

To understand rheumatology health care professionals' (therapists') experiences and views of being trained in and delivering the CBA and PEP interventions as part of the LIFT trial.

#### Study design

An optional nested qualitative process evaluation sub-study with participants and therapists who have taken part in the Lessening the Impact of Fatigue Trial (LIFT).

#### Participants

A subgroup of LIFT study participants randomised to either CBA or PEP will be invited if they have given consent to be contacted after they have completed or stopped their treatment.

All therapists (both PEP and CBA) who were trained and delivered the interventions will receive additional information.

To ensure integrity, participants will be invited to take part once they have left or completed the intervention phase (see Figure 1 main protocol).

#### Participant identification and sample size

We will use a maximum variation sampling strategy [1] to identify participants with a range of IRDs, gender, age, disease duration and primary outcomes in the main RCT. To achieve this, a minimum of 40 interviews (20 per intervention arm) is required. We will aim to invite all study therapists from both intervention arms across all study sites. They will be invited once they have delivered the intervention to their last allocated study participant or once they are suitably experienced based on how long they have been delivering the intervention at the time of interview – whichever comes first.

The study team at the Trial Office will send an invitation consisting of a cover letter, study information, copy of the consent form and reply slip to each potential participant who has

given permission to be contacted after the LIFT study. Participants will be invited after they attended assessment visit 4 at 56 weeks or if they have withdrawn during the followup phase. The study team at the Trial Office will also send invitations to all study therapists.

Participants willing to take part can return the completed Participant Reply Slip sent with the invitation letter directly to the designated study site at the Bristol Royal Infirmary. Therapists willing to take part will get in touch with the designated member of the local study team as per site delegation log by phone or email.

A designated member of the local study team as per site delegation log at the designated study site will contact the potential participant/therapist to discuss the study and arrange a date and time for the interview.

#### Consenting participants and therapists

Once contacted for the interview, at the beginning of the call, the purpose and process of the interview will be explained again, before potential participants are asked to consent. Verbal consent will only considered to have been given at this point and will be recorded on a digital voice recorder. Participants and therapists will have received the wording of the consent as part of their invitation to take part.

#### Interviews and data collection

Data will be collected through semi-structured interviews conducted by telephone or by internet-based audio/video calls. In addition to the practical considerations of offering these options, this approach acknowledges that both participants and therapists will have been involved in a remotely delivered intervention. All interviews will be audio recorded, anonymised during transcription, and checked for accuracy.

#### Participant/therapist withdrawal

Participants/therapists are free to withdraw at any time, and with no explanation. If they withdraw before the findings are written up, we will not include any of their data.

#### Analysis

Participant experiences and views of the interventions will be analysed using a framework analysis [2] to assess the content, mode of delivery, acceptability, barriers and facilitators, helpfulness and subsequent impact of the interventions on their daily lives.

Experiences and views of the therapists of intervention training and delivery, including challenges and benefits of learning and using new skills, and barriers and facilitators to supporting patients remotely will be analysed using inductive thematic analysis [3].

#### Data handling

The study specific database (see 8.2 in main protocol) will be used. Personal contact details will be made available to the designated member of the local study team as per site delegation log at the study site only when the participants have given their permission to be contacted.

Recorded consent will be stored as essential digital documents in a bespoke database provided and maintained by CHaRT (see 8.2 in main protocol) as well as secured shared drives with access via password controlled computers (university) by study staff only (electronic data). At the end of the project, they will be archived in the University of Aberdeen archive (see 14.2 in main protocol).

#### Safety assessments

We do not anticipate any side-effects of taking part in an interview. However, if the interview makes participants feel worried about their fatigue or health, the designated member of the local study team as per site delegation log will arrange for them to see their clinical nurse specialist or rheumatologist.

#### Sub-study matrix

See Figure 1 GANTT chart

1.2 Abbreviations and Definitions

AE	Adverse events
ASDAS	Ankylosing Spondylitis Disease Activity Score
AxSpA	Axial Spondyloarthritis
BILÂG	British Isles Lupus Activity Group
BRAF-MDQ	Bristol Rheumatoid Arthritis Fatigue Multi-Dimensional Questionnaire
CACE	Complier Average Causal Effect
CBA	Cognitive Behavioural Approach
CF	Chalder Fatigue Scale
CHaRT	Centre of Healthcare Randomised Trials
CI	Chief Investigator
CONSORT	Consolidated Standards of Reporting Trials
CRF	Case Report Form
CRP	C-reactive protein
CTU	Clinical Trials Unit
DAS28	Disease Activity Score 28
DMC	Data Monitoring Committee
FSS	Fatigue Severity Scale
HADS	Hospital anxiety and depression scale
IRD	Inflammatory Rheumatic Disease
ITT	Intention to treat
MAR	Missing at random
PA	Physical Activity
PEP	Personalised Exercise Programme
QOL	Quality of Life
RA	Rheumatic Arthritis
RCT	Randomised Controlled Trial
rHCPs	Rheumatology Health Care Professionals
S-VLA	Valued Life Activities short form
SAE	Serious adverse events
SLE	Systemic Lupus Erythematosus
TSH	Thyroid Stimulating Hormone
VBM	Voxel-based morphometry
VO2	Volume oxygen
WPAI:SHP	Work Productivity and Activity Impairment Questionnaire: Specific
	Health Problem

2 Introduction

Despite advances in management of inflammatory rheumatic diseases (IRDs), patients remain burdened by their disease and cite fatigue as a principal problem, equal to pain in terms of burden. Fatigue is a crucial determinant of impaired quality of life (QOL) and a predictor of work disability and indeed the main barrier to remaining in employment. Patients feel this symptom is clinically ignored with rheumatologists admitting ignorance regarding its management.

There is now considerable consensus across the health care community that nonpharmacological interventions, specifically cognitive behavioural approaches (CBA) and programmes designed to support increased physical activity, are valuable treatments to help IRD patients manage the functional challenges such as fatigue.

This statistical analysis plan (SAP) documents the planned analysis for the main Lift Trial

